
2. Objectives (include all primary and secondary objectives)

The project has the following primary and secondary objectives:

Primary Objective

Suppression of viral load. Assess the effectiveness of an empirically-based incentive intervention in maintaining undetectable HIV-1 RNA (viral loads) in people living with HIV.

Secondary Objectives

Adherence to HIV care. Assess the effectiveness of an empirically-based incentive intervention for viral load suppression in promoting biologically-verified adherence to antiretroviral medications, promoting maintenance of prescriptions for antiretroviral medications, and retaining patients in HIV medical care.

Post intervention effects. Assess the effectiveness of an empirically-based incentive intervention for viral load suppression in promoting effects after the intervention is discontinued.

[figure not shown]
Moderators. Determine if drug dependence, alcohol dependence, depression, health literacy, and impulsivity moderate viral load suppression and response to the incentive intervention.

Mediators. Determine if ART adherence as assessed by qualitative HRMS blood tests of 15 antiretroviral medications mediates the effect of the incentive intervention on viral load suppression.

Economic Aims. Assess the costs, cost-effectiveness and cost-benefit of the incentive intervention.

3. Background (briefly describe pre-clinical and clinical data, current experience with procedures, drug or device, and any other relevant information to justify the research)

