Participants (N = 200) who complete the HIV Medical Care Education program will be randomly assigned to a Usual Care Control group or the Incentive group. A computerized urn randomization procedure (Wei & Lachin, 1988) will be used to balance groups on five baseline characteristics that may influence outcome: (1) opiate or cocaine positive urine sample at intake to the study (Y/N); (2) Self-reported use alcohol to intoxication on 20 or more days in the past 30 on the ASI (Y/N); (3) health literacy as assessed on the TOFHLA (score \leq the rolling median, Y/N); (4) impulsivity as assessed by delay discounting (k value from the raw discounting data for each participant, which is an index of impulsivity (\leq the rolling median of k, Y/N); and (5) depression as assessed by the Beck Depression Inventory (score \leq the rolling median, Y/N). Participants will be stratified by DSM V cocaine, opiate and alcohol dependence, health literacy, and depression at intake because drug use (Mimiaga et al., 2013), health literacy (Kalichman et al., 2008), and depression (Murphy et al. 2013) has each been associated with poor ART adherence. Participants will be stratified based on measures of impulsivity because high levels of impulsivity have been associated with poor health decision making and adverse health behaviors (Axon et al. 2009; Bickel et al. 2014; Bradford et al., 2010). Participants will be taught the details of their group with written instructions and quizzes. Participants will earn up to about \$15 for answering questions on the quiz.

Incentive Group

The Incentive group will receive the novel empirically-based incentive intervention to promote long term suppression of HIV-1 RNA (viral load) being evaluated in this study. The incentive intervention will employ features and parameters that have been shown critically important to promote therapeutic behavior change in drug users and other populations (Higgins et al., 2008; Lussier et al., 2006; [name] et al., 2011). Participants will be taught the details of the incentive program with written instructions and quizzes.

A Prescription for ART. When a participant gets assigned to the Incentive group, he/she will be asked if he/she has a current prescription for ART and if he/she has at least a 2-day supply of medication. As described below, blood draws and the incentive program described below will not begin until the participant has an active ART prescription and has at least a 2-day supply of medication.

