visual analog scale (VAS) to assess ART adherence in which participants mark a 100 mm line to indicate their percent adherence to their antiretroviral medications over the previous 4 weeks (Buscher et al., 2011; Walsh et al., 2002). Responses on this VAS have been associated with pill taking with MEMS (Buscher et al., 2011; Walsh et al., 2002), pill count (Walsh et al., 2002), and pharmacy records (Buscher et al., 2011). 7) Assess whether each participant refilled their ART prescription for each month, the pharmacy that filled each prescription, and the medication. 8) Pharmacy records will be obtained (with participant permission) to confirm self-reported data. 9) Participants will be asked how many primary HIV care visits they had in the past 3 months using procedures and definitions used in a prior multisite study (Purcell et al., 2007). Medical records will be obtained with permission to confirm self-reports. 10) The *Modified Economic Form 90 AIR/ED* will be created for this study based on the Economic Form 90 AIR/ED (Bray et al., 2007; Miller and Del Boca, 1994; Scheurich et al., 2005; Tonigan et al., 1997) to collect patient data on all health care utilization within the past 180 days. 10) A Modified SASCAP (Zarkin, Dunlap et al. 2004) will be used to estimate the costs associated with services in the study conditions. The SASCAP (www.rti.org/sascap) assesses activity-level resource use and cost data for intervention staff, consultants, and non-labor resources (e.g., building space) used in the provision of intervention services. The SASCAP method reliably estimates the costs of intervention activities and the cost per participant. Zarkin and Dunlap have applied this micro-costing approach (Zarkin et al., 2003, 2005, 2008, 2010; Dunlap et al., 2010). 11) A multiple-choice test evaluating the HIV Education Course.

b. Study duration and number of study visits required of research participants.

Participants in the incentive group will receive the incentive intervention for two years. For all participants, assessments will be conducted at intake to determine eligibility and characterize participants. Outcome assessments will be conducted at intake, every 3 months throughout the 2-year intervention evaluation and every 6 months of the 1-year follow-up period.

c. Blinding, including justification for blinding or not blinding the trial, if applicable.

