a. Primary outcome variable.

Specific Aim. Assess the effectiveness of an empirically-based incentive intervention in maintaining undetectable viral loads in people living with HIV. We will assess the percentage of blood samples that have undetectable viral loads (i.e., <200 copies/mL) at the eight 3-month assessments conducted throughout the 2-year intervention evaluation period (Y/N at each assessment).

a. Secondary outcome variables.

We expect that the incentive intervention could affect measures that are not directly targeted by the intervention. Since patients must adhere to ART and stay in HIV care to achieve undetectable levels of viral load, we expect that the incentive intervention will increase consistent adherence to ART, maintenance of prescriptions for ART, and retention in HIV medical care. It may also produce post-intervention effects.

Specific Aim. Assess the effectiveness of an empirically-based incentive intervention for decreased or undetectable viral loads in promoting biologically-verified adherence to antiretroviral medications. We will assess whether the participant maintained consistent ART adherence by conducting qualitative high-resolution mass spectrometry (HRMS) blood tests of 15 antiretroviral medications. Participants will be considered adherent if they test positive for all of their prescribed medications (Y/N at each 3-month assessment).

Specific Aim. Assess the effectiveness of an empirically-based incentive intervention for decreased or undetectable viral loads in promoting self-reported adherence to antiretroviral medications. We will assess whether the participant reports maintaining consistent ART adherence by reporting taking >90% of all scheduled doses in the past 30 days (Y/N at each 3-month assessment based on responses on a visual analog scale to assess adherence to antiretroviral medications, see below).

Specific Aim. Assess the effectiveness of an empirically-based incentive intervention for decreased or undetectable viral loads in maintaining prescriptions for antiretroviral medications. We will assess the percentage of months that the participant refilled a prescription for antiretroviral medications throughout the 2-year intervention evaluation period (Y/N for each month prior to each 3-month assessment based on timeline follow-back self-report and confirmed by pharmacy records).

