Primary outcome analyses. We will fit a longitudinal logistic regression model $\text{logit}(Y_{ij}) = \beta_0 + \beta_1 tx + \beta_{2-6}x_{2-6} + \epsilon_{ij}$, where Y_{ij} is the presence of a detectable viral load for the i th person at the j th timepoint (8 visits over two years of treatment), β_1 is the covariate of interest representing the expected decrease in log odds of a detectable viral load as a function of assignment to the treatment group, and β_{2-6} are the coefficients for the 5 randomization covariates. Additional models with time and time by treatment interactions will be fit secondarily to assess time trends in treatment effect.

Secondary outcome analyses. We will fit analogous longitudinal logistic regression models for HRMS-verified ART adherence, self-reported adherence, prescription maintenance, and attendance at HIV medical care visits. We will assess post-treatment effects by fitting analogous models for each outcome, but using only data from the two post-treatment visits.

Moderator analyses. For the primary outcome, we will fit models with interactions between treatment and each of the 5 randomization covariates (drug dependence, alcohol dependence, TOFHLA total score, delay discounting, and Beck Depression score) to assess whether treatment effect varies as a function of the putative moderator. For example, for CIDI drug dependence, we would fit the model $\text{logit}(Y_{ij}) = \beta_0 + \beta_1 tx + \beta_{2-6}x_{2-6} + \beta_7 tx * \text{drug dependence} + \epsilon_{ij}$, where β_1 would represent the treatment effect (expressed as a difference in log odds of a detectable viral load between treatment and control groups) among individuals without drug dependence, and β_7 would represent the difference in treatment effect between individuals with and without drug dependence. All moderator analyses will be considered exploratory and will not be corrected for multiple comparisons. These variables will be examined as potential moderators because drug use (Mimiaga et al., 2013), health literacy (Kalichman et al., 2008),

and depression (Murphy et al. 2013) has each been associated with poor adherence to antiretroviral medications. Impulsivity will be assessed as a potential moderator because high levels of impulsivity have been associated with poor health decision making and adverse health behaviors (Axon et al., 2009; Bickel et al. 2014; Bradford et al., 2010).

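### Prescription maintenance counts months with a refill, not months with ART on hand; if multi-month supplies are dispensed, this secondary outcome is understated and the arm difference can be biased either way

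*Combined protocol and SAP*

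**What the plan says.** The secondary objective in section 2 concerns "promoting maintenance of prescriptions for antiretroviral medications". Section 7 (Secondary outcome variables) turns this into a rule: "We will assess the percentage of months that the participant refilled a prescription for antiretroviral medications throughout the 2-year intervention evaluation period". The scoring is given as "Y/N for each month prior to each 3-month assessment based on timeline follow-back self-report and confirmed by pharmacy records".

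The data come from items 7 and 8 of the follow-up assessments in section 4a. Item 7 reads: "Assess whether each participant refilled their ART prescription for each month, the pharmacy that filled each prescription, and the medication". Item 8 reads: "Pharmacy records will be obtained (with participant permission) to confirm self-reported data". Quantity dispensed and days supplied are not listed, and no rule carries supply forward from one month to the next.

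The analysis in section 7 (Secondary outcome analyses) is: "We will fit analogous longitudinal logistic regression models for HRMS-verified ART adherence, self-reported adherence, prescription maintenance, and attendance at HIV medical care visits". The post-treatment aim applies the same measures at the two 6-month assessments in the year after the intervention.

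**The concern.** The aim is to learn whether incentives help "in maintaining prescriptions for antiretroviral medications". A refill in a given month shows this well only when each fill lasts about one month. With longer fills, months that are fully supplied but contain no refill are scored N. The rule then cannot separate a participant who always has medication and fills every three months from one on 1-month fills who has no medication two months in three.

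Nothing later in the plan corrects this. A covered month without a refill is an observed N, not a missing value, so comparing results with and without imputation (section 7, Missing data) would not show it. Pharmacy records used only to confirm that a refill took place would confirm both participants' scores. At stake is the interpretation of one named secondary aim and of its post-treatment counterpart.

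**Working it through.** **The plan's own figures.** The plan gives no expected rate, effect size or power for prescription maintenance, so there is no figure to reproduce for this outcome. The power analysis concerns the primary outcome (15 points; 200 × 0.80 = 160) and does not depend on this measure. The 15 points are borrowed below for illustration only.

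**Inputs from the documents.** 24 months of intervention; Y/N per month for a refill; effects expressed as odds ratios.

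**Inputs assumed.** Supply lengths of 1, 2, 3 and 6 months; true coverage of 60% (control) and 75% (Incentive); the share q of covered time supplied by 3-month fills. The only supply amount in the documents is the condition for starting the incentive program, that the participant "has at least a 2-day supply of medication".

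**Step 1: one continuously covered participant, all 24 months scored.** Score = (24/s)/24 for an s-month supply.

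- s = 1: 24/24 = 100%
- s = 2: 12/24 = 50%
- s = 3: 8/24 = 33.3% (90-day fills over 730 days fall in 8 or 9 months, so 33.3% to 37.5%)
- s = 6: 4/24 = 16.7%

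The scoring phrase could also mean only the month just before each of the eight visits. A participant on a regular 3-month cycle would then score 0/8 or 8/8, depending on when the cycle falls.

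**Step 2: arm level.** Three-month fills register one covered month in three, so observed score = true coverage × (1 − 2q/3). The odds ratios are unadjusted, computed from the two proportions.

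| q control | q Incentive | Control | Incentive | Difference | OR |
|---|---|---|---|---|---|
| 0 | 0 | 60.0% | 75.0% | 15.0 | 2.00 |
| 0.10 | 0.10 | 56.0% | 70.0% | 14.0 | 1.83 |
| 0.25 | 0.25 | 50.0% | 62.5% | 12.5 | 1.67 |
| 0.50 | 0.50 | 40.0% | 50.0% | 10.0 | 1.50 |
| 0 | 0.20 | 60.0% | 65.0% | 5.0 | 1.24 |
| 0.20 | 0.10 | 52.0% | 70.0% | 18.0 | 2.15 |

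Example, second row: 0.60 × (1 − 0.20/3) = 0.560; 0.75 × (1 − 0.20/3) = 0.700; OR = (0.70/0.30)/(0.56/0.44) = 1.83.

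**Step 3: what a reversal would need.** Setting the observed scores equal gives q(Incentive) > 1.5 × [1 − p(control) × (1 − 2q(control)/3)/p(Incentive)].

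- True 60% vs 75%: above 0.30 with no control use; above 0.46 with control use of 0.20.
- True 50% vs 65%, no control use: above 0.35. True 70% vs 85%, no control use: above 0.27.
- A smaller true difference, 70% vs 80%, with control use of 0.10: 1.5 × (1 − 0.6533/0.80) = 0.275, a gap of 17.5 points between arms.

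**Step 4: with the rule changed.** If a month counts when supply covers it, the continuously covered participant scores 24/24 at any supply length, and the assumed contrast stays at 15 points (OR 2.00).

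**The case against.** The strongest objection is that the premise lies outside the documents: nowhere do they say that ART is dispensed for more than a month at a time. Entry requires a detectable viral load and admits people not in care. If longer supplies go mainly to stable patients, they may be uncommon, at least early on. This stands, and it makes the size of the problem conditional.

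Second, item 7 in section 4a speaks of refilling for each month, which could mean that the month was supplied. No rule says so, the outcome definition in section 7 counts months in which a refill was made, and coverage cannot be derived from the items listed. The reading is possible, but the plan would need to state it.

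Third, refill behaviour is a legitimate measure in its own right, and drug-taking is captured separately by the blood tests and the visual analog scale. That limits the harm, but it does not make a covered month without a refill a failure to maintain a prescription. It is also fair that, where the pharmacy records hold days supplied, coverage could still be scored at analysis. The gap is then the stated rule and the participants without records.

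A reader might go further and infer that the measure penalises the Incentive arm, or that the effect will reverse. The documents do not support this. They contain no evidence that supply length would differ by arm, equal use shrinks the difference without reversing it, and higher use in control inflates it. Nor is one third a floor; it is simply the 3-month case.

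**Conclusion.** The point holds as an inexpensive improvement to one secondary outcome and its post-treatment version. As written, the rule counts refill months, and neither the listed data items nor the planned analyses correct for supply length. The size depends on an assumption that the documents neither confirm nor exclude, namely that multi-month supplies are dispensed. On the assumed 60% versus 75%, equal use of 3-month fills up to 50% costs 1 to 5 of the 15 points; unequal use can move the difference in either direction. Reversal is an extreme case that needs a large gap in supply length between arms. The primary outcome and the sample size of 200 are not touched.

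**What to change.** Redefine the outcome: a month is Y if ART supply was on hand for it, computed from fill date plus days supplied and carried forward, using the pharmacy records already requested. Fix the days-covered threshold in advance, for example 80% of days in the month. Add a question on days supplied to the refill item, for use where records are missing. State that all months in each interval are scored, not only the month before the visit, and apply the same rule to the two post-treatment assessments.

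The cost is one extra data field, one extra question and a little more data entry. If multi-month fills turn out to be absent, little is lost.

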Specific Aim. Assess the effectiveness of the incentive intervention for decreased or undetectable viral loads in promoting retention in HIV medical care. We will assess whether the participant attended at least 2 medical visits per year (Mugavaro et al. 2012; Y/N each year based on self-report and medical records).

Specific Aim. Assess the effectiveness of an empirically-based incentive intervention in promoting undetectable levels of viral loads, maintenance of antiretroviral prescriptions, consistent adherence to antiretroviral therapy, and retention in HIV care after the incentive intervention is discontinued. We will assess measures described above but at the two 6-month assessments during the year after the intervention ends.

Moderator Analysis Measures

Specific Aim. Determine if drug (cocaine or opiate) dependence, alcohol dependence, depression, health literacy, and impulsivity assessed at intake moderate viral load suppression and response to the incentive intervention. A dichotomous value (Y/N) for cocaine, opiate and alcohol dependence will be used as assessed by the CIDI. The total score on the TOFHLA will be used to assess health literacy. The total score on the Beck Depression Inventory will be used to assess depression. Log transformed k for each participant on the delay discounting task will be used to assess impulsivity.

Mediator Analysis Measures

Specific Aim. Determine if antiretroviral medication adherence as assessed by qualitative HRMS blood tests of 15 antiretroviral medications mediates the effect of the incentive intervention on viral load suppression. We will assess mediating effects of medication adherence as assessed by qualitative blood testing on viral load using the method of Baron and Kenny (1986) as described below.

Economic Outcome Measures

Specific Aim. Assess the costs of HIV medical care for Usual Care and Incentive groups. We will assess the total cost per participant of both study interventions including cost of the incentive program (see below). We expect that Incentive group costs will be higher relative to the Usual Care due to the incentive program and because we expect that the Incentive participants will have greater treatment engagement.

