Mediation analysis. We will assess potential mediating effects of medication adherence as assessed by qualitative blood testing on viral load using the method of Baron and Kenny (1986). Specifically, this involves estimation of (1) the effect of treatment assignment (incentives) on undetectable viral load without controlling for medication adherence, (2) the direct effect of incentives on medication adherence, and if these two steps yield clinically and statistically significant effects, 3) the effect of incentives on viral load after controlling for medication adherence ($\text{logit } (Y_{ij}) = \beta_0 + \beta_1 x_i + \beta_{2-6} x_{2-6} + \beta_7 \text{adherence} + \epsilon_{ij}$). If medication adherence does mediate the effect of the incentives on presence of a detectable viral load, in this final model we would expect the effect of treatment (β_1) to be attenuated relative to the step 1 model, and for adherence (β_7) to be a clinically and statistically significant predictor of presence of a detectable viral load.

Missing data. We expect to collect $\geq 80\%$ of 3-month assessments (see below). Our primary approach will be to impute all missing values as the adverse outcome (e.g., detectable viral load). Model parameter estimates from this approach will be compared to a method without imputation. If these methods yield differing results, conclusions will need to be tentative. To investigate sensitivity to missing values, participants with and without missing values will be compared by covariates and treatment assignment.

ECONOMIC ANALYSES

We will use the provider perspective using a modified SASCAP and the research team's financial records. Intervention activities will be captured with the modified Economic Form 90 AIR/ED.

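### As written, a missed interview can be scored as no refill for months in which a pharmacy record shows a refill; retention is affected less, and its source wording needs reconciling

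*Combined protocol and SAP*

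**What the plan says.** **Refill.** Section 7a (secondary outcomes, prescription maintenance) scores "Y/N for each month prior to each 3-month assessment", "based on timeline follow-back self-report and confirmed by pharmacy records". The assessment list in Section 4a gives the records the same supporting role: "Pharmacy records will be obtained (with participant permission) to confirm self-reported data".

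**Retention.** Section 7a sets the threshold: "We will assess whether the participant attended at least 2 medical visits per year". It gives the source as "Y/N each year based on self-report and medical records", naming both side by side. Section 4a differs. There the visit count comes from the interview ("Participants will be asked how many primary HIV care visits they had in the past 3 months") and the records are secondary: "Medical records will be obtained with permission to confirm self-reports".

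**Missing data.** Section 7b states: "Our primary approach will be to impute all missing values as the adverse outcome". Detectable viral load is given as an example, not as a limit. A comparison without imputation is planned, and so is a comparison of participants with and without missing values by covariates and treatment assignment.

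The plan does not say whether a month counts as missing when the interview was missed but a record exists. It does not say whether records are sought for quarters without an interview, or which source prevails when the two disagree.

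**The concern.** Refills and clinic visits leave records whether or not the participant attends a study interview. If the interview is the source and the record only confirms it, a missed interview leaves nothing to confirm. The general imputation rule then supplies a failure. The refill outcome becomes partly a measure of interview attendance. Equal missingness in the two arms dilutes a true difference. Unequal missingness can enlarge it, hide it, or create one where none exists.

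Unequal attendance is plausible. Incentive participants make paid weekly calls and give frequent blood samples, controls have no such contact, and participants are not blinded. On the other side, assessment payments are the same in both groups (Section 9). The documents do not settle the direction.

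**Working it through.** **Inputs from the plan.** 200 randomised; 20% missing (Section 7b, Power Analysis); at least 80% of 3-month assessments expected (Section 7b, Missing data); 24 months of intervention; retention threshold of 2 visits per year.

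**The plan's own figure.** 200 x 0.80 = 160, as stated. That calculation concerns the primary outcome. The plan gives no figure for refill or retention.

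**Assumptions.** The true refill rates (80% vs 70%, and 75% in both arms) and the 15%/25% split by arm are illustrative. Records are taken as unused for missed interviews. The true refill rate is taken to be the same in missed and attended months; if those who miss interviews refill less often, the loss is smaller.

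**Refill.** Scored rate = p x (1 - m), with p the true rate and m the share of months whose interview was missed. At m = 0.20, an average of 24 x 0.20 = 4.8 months per participant are scored as no refill regardless of the record. OR = [a/(1-a)] / [b/(1-b)], with a and b the scored incentive and control rates, unadjusted.

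| True rate, incentive / control | Missed, incentive / control | Scored incentive | Scored control | Difference (points) | OR |
|---|---|---|---|---|---|
| 80% / 70% | none | 80% | 70% | +10 | 1.71 |
| 80% / 70% | 20% / 20% | 0.80 x 0.80 = 64% | 0.70 x 0.80 = 56% | +8 | 1.40 |
| 80% / 70% | 15% / 25% | 0.80 x 0.85 = 68% | 0.70 x 0.75 = 52.5% | +15.5 | 1.92 |
| 80% / 70% | 25% / 15% | 0.80 x 0.75 = 60% | 0.70 x 0.85 = 59.5% | +0.5 | 1.02 |
| 75% / 75% | 15% / 25% | 0.75 x 0.85 = 63.75% | 0.75 x 0.75 = 56.25% | +7.5 | 1.37 |
| 75% / 75% | 25% / 15% | 56.25% | 63.75% | -7.5 | 0.73 |

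**Effect of the fix.** If records fill a share r of the missed months, scored rate = p x [1 - m x (1 - r)]. At 20% missing in both arms and r = 0.5: 0.80 x 0.90 - 0.70 x 0.90 = 0.72 - 0.63 = +9 points. At r = 1 the full +10 returns.

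**Retention, if only completed interviews counted.** With one visit per quarter and interviews missed independently at 20%, at least 2 visits are still counted unless 3 or 4 of the 4 interviews are missed: 1 - 0.2^4 - 4 x 0.8 x 0.2^3 = 1 - 0.0016 - 0.0256 = 97.3% of person-years. With irregular visits the loss is larger. Under Poisson visits averaging 2, 3 or 4 per year, the share counted as retained is 46.7%, 67.0% or 79.8%, against true shares of 59.4%, 80.1% or 90.8%. These are upper bounds on the loss, because the definition in Section 7a also names medical records.

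**The case against.** The strongest objection is that the plan never says a month with a pharmacy record but no interview is missing. The imputation rule applies to missing values without tying them to interview attendance, and a sensible analyst might use the record. That stands as a limit on the claim: the documents permit this scoring but do not state it. It does not remove the problem, because both places that describe pharmacy records give them a confirming role only and the imputation rule has no exception.

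A reader might also infer that one missed interview makes a participant not retained, or that only the 0.8^4 = 41% of person-years with all four interviews could be scored correctly. The documents do not support this. Retention is yearly, needs 2 visits, and names medical records in its definition; nothing requires four interviews.

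A missed quarter may also be partly recoverable. The health care utilisation form in Section 4a looks back 180 days, and the refill follow-back is not said to exclude earlier months. Neither is stated to feed these outcomes after a missed interview. The plan does take viral load and CD4 results from medical records where possible (Risks, item a), so using records in place of study collection is not foreign to it.

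The planned comparison without imputation, and the comparison of missingness by arm, would help reveal unequal missingness. They do not repair it: the first drops the affected months and does not use the record.

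Finally, records are not complete truth. The dispensing pharmacy is itself asked about at the assessment, so after a missed interview it may be unknown or changed. This stands, and it shapes the fix.

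**Conclusion.** The point holds for refill. As written, the plan lets the missing-as-failure rule override a pharmacy record. At 20% missing in both arms, an assumed 10-point difference is scored as 8. With an assumed 15%/25% split it is scored anywhere from 0.5 to 15.5, and with no true difference a spurious 7.5 points appears in either direction. Only the 20% comes from the plan. The true rates, the split, non-use of records and equal refill in missed and attended months are assumptions, and the documents support neither direction of imbalance.

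For retention the finding is narrower. Sections 4a and 7a describe the role of medical records differently and must be reconciled; a missed interview does not by itself mean not retained. It would be too strong to say that the plan definitely scores recorded refills as failures, or that the two outcomes are equally affected. Both are secondary, and the primary viral load outcome is not touched by this point.

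**What to change.** In Sections 4a and 7, state a source rule for both outcomes:

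1. For every randomised participant who gave permission, obtain pharmacy and medical records for the whole period, whether or not interviews were attended.
2. When the interview is missed, let a record of a refill or visit determine the outcome.
3. Use self-report where no record can be obtained, and say which source prevails when the two disagree.
4. Define a value as missing only when neither source is available, and apply the adverse-outcome imputation only then.
5. Do not treat the absence of a record from an unidentified pharmacy as proof of no refill.

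Use the same wording for retention in both sections.

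The cost is SAP and protocol wording plus some extra record handling, since records are already to be obtained with permission. Two practical limits remain. Records may be incomplete where the pharmacy changed. The permission also needs checking: the release described at screening covers eligibility, medications used and description of the population, so it should be confirmed that it extends to outcome data for quarters without an interview.
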